Encouraging findings in other areas of medicine have motivated researchers to turn their attention to better understanding the complex ways in which nature interacts with nurture to produce schizophrenia. This genotype x environmental interaction (GxE) approach differs from the linear gene-phenotype approach by positing a causal role not only for either genes or environment in isolation, but also for their synergistic co-participation in the cause of schizophrenia where the effect of one is conditional on the other (130, 131). For example, genes may moderate the effects of certain drugs of abuse, or the environment may moderate the level of expression of a gene associated with schizophrenia. The current study will collect biological samples of blood and CSF for genetic analysis in order to investigate whether GxE interactions predict outcome and moderate/mediate response to treatment. This will build on the work of studies currently underway, such as the European Union-Gene Environment Interaction in the Onset of Schizophrenia Study (https://www.eu-gei.eu), which Orygen is participating in.

Owing to the relatively invasive nature of CSF collection via lumbar puncture, it would be preferable if C4 levels could be monitored in plasma. However, seeing that C4 and other complement proteins are not thought to cross the blood-brain barrier, measuring the plasma levels of C4 might not accurately reflect the levels of C4 in the CSF. In order to assess this,

our collaborators at The Broad Institute sought to understand the extent to which plasma C4 levels might have information about CSF C4 levels, since this route would ask less of research participants. They measured C4 levels in CSF and plasma samples from the same 50 donors, asking whether CSF and plasma levels of C4 are correlated across individuals. They found that although CSF and plasma levels of C4 each exhibit substantial inter-individual variation, the inter-individual variation in these two compartments is almost completely uncorrelated. For example, the five individuals with the greatest elevation in CSF C4 levels (five times the median CSF C4 level), all had below-average levels of C4 in their plasma samples. These results suggest that plasma analysis will have little information about C4 levels in CSF. Based on these results, we have concluded that analysis of CSF is crucial for monitoring CNS-relevant levels of C4.

We do not specify the exact genes (or more appropriately, genetic markers) to be analysed in this study. This is for two reasons: i) much of genetic research at present is 'genome-wide', i.e. is not hypothesis driven but based on unbiased discovery approaches. Our study will include genome-wide hypothesis generating approaches (such as proteomic or gene expression analysis) which would generate novel genes to look at and therefore it is not possible to say in advance which genetic markers we will examine, ii) the field is changing very quickly; new polymorphisms which are associated with schizophrenia are emerging at an increasing pace. We will use specific genetic polymorphisms including known schizophrenia risk alleles (for example those near TCF4, CACNA1C, TCF7L2, HLA, ZNF804A, miR137) and CNVs (deletion sin neurexin 1, 15q13.3 etc.) and also include novel genetic polymorphisms that might emerge during the lifetime of the project.

It is important to translate such genetic and biological findings into tools and therapies that can contribute to the diagnosis and treatment of patients. While measurements of RNA in *post mortem* brain tissue are useful for determining biological mechanisms, they are not clinically useful because they can only be obtained from brain tissue post mortem. It would be far more valuable clinically to have biomarkers for risk or progression that could inform the care of living individuals, that could be obtained without sampling brain tissue, and that could be used to monitor dynamic biological processes that unfold over time – such as adolescent synaptic pruning and other sequelae of neuron-microglia interactions. As indicated above, C4 RNA expression holds promise for being such a biomarker. Such biomarkers would also facilitate the evaluation of future, innovative therapeutics that seek to modulate these processes.

"SMART" Study Design

Creating an evidence base fit for implementation and for subsequent clinical translation requires a trial methodology which experimentally evaluates interventions via multistage designs, and which builds upon methods intended for the analysis of naturalistically observed strategies. A clinical trial design innovation, the Sequential Multiple Assignment Randomized Trial ("SMART"), used in several recent large scale studies in psychiatry to develop an evidence base to support adaptive clinical care, is a good fit with the clinical staging model, and is ideal for the present study. SMART designs involve multiple intervention stages that correspond to the critical decisions involved in adaptive interventions. Adaptive interventions are interventions in which the type or dosage of the intervention is individualised on the basis of patient characteristics or clinical presentation and then are repeatedly adjusted over time in response to patient progress (132). Interventions can also be tailored at critical decision points according to response or other patient characteristics such as specific biomarker changes or comorbidity, and also patient preference (133). Using this approach, the study should have important implications for clinical practice, as the clinical situation often requires decisions about how to adapt the intervention based on patient progress or preference.

Internationally Unique Stigma-free Enhanced Primary Care Platforms

The Australian "headspace" system is a nationwide platform of care for young people, which has already enabled access to clinical and social care to over 100,000 young Australians aged 12 – 25 years (inclusive) with emerging mental ill health. The system is essentially a "one stop shop", universal access model for young people and families experiencing early stage mental and substance use disorders. Our research centre conceived, designed and implemented this reform from 2006-2009, and it has now expanded across the nation to 70 centres and will expand to 100 centres by 2016. Some early literature and data on the headspace model have been published (133-136). Orygen directly operates 4 of these platforms with an annual throughput of over 5000 young people. Unpublished research data gathered from these sites (n=800) indicate that 38% of the patients meet the UHR criteria. We recently reported on a large baseline cohort of patients (n=21,274) assessed through the full headspace system of care nationally (137).

Understanding engagement and ethical concerns: In studies among persons at-risk of psychosis, several ethical dilemmas have been identified (160). For those young people at risk of psychosis, both being identified as being at risk and receiving interventions can be explored further within the four ethical principles of a) beneficence, b) non-maleficence, c) respect for autonomy and d) justice. Overall, for risk identification and preventive interventions, the balance of benefits and risks should be balanced against principles of autonomy, with a broader consideration of principles of distributive justice (161). Despite the explosion of research information regarding risk prediction for psychosis, very little is

known about participants' perspectives regarding being at-risk. While several studies in psychosis prediction include participants who are at risk, there is little information on how much they understand about the nature of risk, and the uncertainties regarding risk for serious mental disorders. Their appreciation of the balance of risks and benefits is also poorly studied.

While such assessment would be important with respect to young people at risk, it may also be important to consider their parents, as the legal guardians. A previous qualitative study indicated that when young people were considered to be at risk of future mental disorders, parents expressed a preference for these young people to not know that they are at a greater risk (163). Thus, a first step would be to understand parents' understanding of young people's risk as well as the various ethical imperatives associated with risk identification. This could be followed up with a future study that explores similar issues among young people, incorporating parents' views.

4.2. Study Rationale

Given the background outlined above, we propose a carefully formulated program of translational research with two linked elements. The first element is designed to create new knowledge and skills for intervening in the early clinical stages of psychotic disorders. The heterogeneity of the UHR stage of illness means that individualised "adaptive" treatment policies are required and a SMART design indicated. Some patients will respond while others will not to the same intervention type, intensity or duration. Other reasons in support of adaptive and sequential approaches include the need for sample enrichment, changing responsiveness linked to stage of illness, presence of comorbidities and the high risk of relapse even when initial remission has been achieved (24).

The second element involves the processing of this emerging new evidence and experience and adapting and translating this to key parts of the US health care system. This will be the subject of a separate Human Research and Ethics Committee application in the US. Through a series of focus groups with key stakeholders, potential challenges and solutions to US implementation across public and private healthcare will be identified. Open-label use of the study interventions in a UHR outpatient clinic in the US will assess the feasibility and acceptability of the staged intervention model and study treatments.

This model of research is ambitious and, due to the target clinical phenotype and the potential cost-effective impact, could be truly ground-breaking. Collectively this group of investigators has the most extensive cumulative experience and track record in this research field, the most congruent research design, and we have assembled for the first time the necessary clinical infrastructure and methodology to enable this research program to be

successfully completed and its findings to be translated into US healthcare. The investigators believe that this Australian-US collaboration is ideally placed to make this much-needed and now achievable contribution to new knowledge, to evidence informed care in early intervention and to enhanced patient and family outcomes.

In summary, the proposed study's sequential multi-stage design is intended to produce evidence to guide a stepwise clinical approach to treatment of UHR patients and reduction of risk for psychosis and other deleterious clinical and/or functional outcomes. The study will also collect data on key biomarkers and other mechanisms potentially underpinning risk, which may ultimately be used to adapt and personalise treatment. Major recent service reforms and expansions in Australia have enabled our research centre to access much larger clinical samples through which we can make a crucial contribution to assembling an evidence base that, with the assistance of the US investigators, will be translatable to US health care, and other settings worldwide with the goal of reducing the enormous human, social and economic costs of schizophrenia and other psychotic disorders.

581 582 583

584

585

586

587

588

589

572

573

574

575

576

577

578

579

580

An examination of parents' perspectives and beliefs about their children being identified as at risk for psychosis, or other serious mental disorders would be enlightening within the context of this study. This information could be key to improving the process of obtaining consent in prediction research and disseminating clinical and research information regarding participants being at-risk. This could also lay the foundation for future research which could help clinicians and researchers discuss information regarding new interventions in at-risk participants and in turn help new interventions such as decision aids.

590 **4.3. Study Aims**

- 591 The main study aim is to test outcomes of UHR patients, primarily functional outcome, in
- response to a sequential intervention strategy consisting of Support and Problem Solving
- 593 (SPS), Cognitive-Behavioural Case Management (CBCM), and antidepressant medication. A
- 594 secondary aim is to test biological and psychological variables that moderate and mediate
- response to this sequential treatment strategy.
- 596 4.4. Hypotheses
- 597 **Hypothesis 1:** In Step 1 we hypothesize that 50% of (500) initial participants will respond to
- the open label SPS intervention.
- 599 **Hypothesis 2a**: In Step 2 (n≥200), we hypothesize that there will be a significantly better
- 600 response (on the primary outcome of functioning) to Cognitive Behavioural Case
- 601 Management (CBCM) than to SPS.
- Secondary hypotheses for Step 2 are as follows:

- In the CBCM group, baseline cognitive biases and vulnerabilities will predict response and outcome (**H2b**), and those with better outcome and responders will show a significantly greater change on these variables than those with worse outcome (**H2c**) and non-responders (**H2d**).
- Hypothesis 3: In Step 3 (estimated n=80), antidepressants will result in a significantly better outcome and greater response than placebo. The fast-fail subgroup is a naturalistic phase and no specific hypothesis is advanced.
- Hypothesis 4: For the relapse prevention arm of the study extending over a period from 6 weeks after the start through to the end of the first year of the study, depending on the point of entry, we hypothesize that those receiving SPS will show a significantly reduced rate of relapse compared to the monitoring only group.

614 4.5. Study Objectives

615

616

617

618

619

620

621

622

623

624

625

626

634 635

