Secondary Objectives	 To test the effect of a sequential treatment approach consisting of SPS, CBCM and antidepressant medication on functioning levels of UHR patients 12 months from baseline (end of Step 3). To test the effect of a sequential treatment approach consisting of SPS, CBCM and antidepressant medication on transition to psychotic disorder by 12 months and 24 months from baseline. To test the effect of a sequential treatment approach on UHR status (maintenance versus remission) 1.5 months, 6 months, 12 and 24 months into treatment. To test the effect of a sequential treatment approach in UHR patients on level of psychiatric symptomatology,

Item	Description				
	including positive psychotic symptoms, negative psychotic symptoms and depressive symptoms 1.5 months, 6 months, 12 months and 24 months into treatment. To test relapse rates (to UHR Positive (UHR+) status) in the relapse prevention/responder arm of the trial (SPS v monitoring) during the first 12 months.				
Exploratory Objectives	The study will explore moderators and mediators of response to treatment with a view to identifying vulnerability markers and mechanisms of therapeutic action. In the subset of responders to a specific intervention, we will examine whether it is likely that the treatment was effective due to putative psychological and neurobiological mechanisms. We will measure psychological variables at baseline, entry and exit from steps two and three and inflammatory and oxidative stress-related biomarkers, as well as antibodies to infectious agents, complement proteins and immunoglobins, at baseline, entry and exit from step three to test whether these variables moderate or mediate response to treatment.				
Study Endpoints	Primary Global Functioning at 6 months (end of Step 2). Secondary Symptoms and functioning 1.5 months into treatment (end of Step 1). Symptoms 6 months into treatment (end of Step 2). Symptoms and functioning 12 months into treatment (end of Step 3). Symptoms and functioning 24 months post baseline (end of follow-up period).				
Study Population	Males and females 12-25 years of age who meet UHR criteria.				
Inclusion Criteria	 Age 12 -25 years (inclusive) at entry. Ability to speak adequate English (for assessment purposes). Ability to provide informed consent. Meeting one or more UHR for psychosis groups as defined in Table 1. 				
Exclusion Criteria	1. Past history of a treated or untreated psychotic episode of				

lkow	Description

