4.5.3. Exploratory Objectives

The study aims to also explore whether there is a relationship between treatment response and specific patient profiles. In the subset of responders to a specific intervention, such as

- 638 CBCM or antidepressants, the study will examine whether it is likely that the treatment was 639 effective due to the proposed putative mechanisms (cognitive biases and neuroprotection).
- We will measure psychological variables at baseline, entry and exit from steps two and three and inflammatory, neuroendocrine and oxidative stress-related biomarkers, as well as antibodies to infectious agents and complement proteins at baseline, entry and exit from step three to test whether these variables moderate or mediate response to treatment.

It is expected that responders to CBCM will be those with more prominent cognitive biases and vulnerabilities at baseline, and which would improve in response to CBCM. The study will also investigate whether response to SPS or CBCM in Step 2 is mediate/moderated by degree of therapeutic alliance (quality of therapeutic relationship) between the participant and clinician. The study will also investigate whether CBCM and SSRIs have any impact on inflammatory and/or neuroendocrine, antibodies to infectious agents, complement proteins and oxidative stress biomarkers. Based on the background material reviewed above, we will also examine whether neurocognition, CSF complement proteins and genetic variables predict outcome (persistent attenuated psychotic symptoms, transition to psychosis, poor functioning) and moderate/mediate response to treatment. Since schizophrenia/psychosis and other deleterious clinical and/or functional outcomes (e.g., persistent severe mood and anxiety disorders) have a biological basis, in addition to psychosocial contributing factors, thorough investigation of potential biomarkers, informed by recent major breakthrough scientific findings (127) using cutting edge technologies, is highly warranted in a study of the present scope and scale. In the parents' study, we will also aim to explore the parent's experience of their child being identified to be at-risk for a major mental illness and their appreciation of autonomy in young people's risk identification and interventions. We will also explore their understanding of the balance between beneficence, risks and autonomy in the different STEP interventions and their preferences for future interventions.

662663

664

665 666

667

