- Moderators and mediators of response: In addition to testing the efficacy of the treatments in Steps 2 and 3 we will be exploring as a secondary aim whether there is a relationship between response and specific forms of treatment. Hence in the responders to a specific intervention such as CBCM or antidepressants, we will address whether the treatment is likely to be working through the putative mechanism proposed. We will measure psychological variables, inflammatory and oxidative stress, antibodies to infectious agents, complement proteins and immunoglobins, and related biomarkers at baseline, entry and exit from steps two and three. We expect that responders to CBT will be those with more prominent cognitive biases and vulnerabilities at baseline, and which would improve in responders to CBT. We will also examine: i) whether CBCM has any impact on inflammatory and/or oxidative stress biomarkers, as well as antibodies to infectious agents, complement proteins and immunoglobins, ii) whether neurocognition and genetic variables predict outcome (persistent attenuated psychotic symptoms, transition to psychosis, poor functioning) and moderate/mediate response to treatment (e.g., whether COMT Val158Met polymorphism influences CBCM response).
- 781 **Response:** The definition of response is as follow:
- The Global Rating Scale or the Frequency score need to be less than 3 for all of the four
 positive symptoms (UTC, NBI, PA and DS) and
- There is an improvement of at least 5 points in SOFAS compared with baseline or the SOFAS score is at least 70.
- The response status will be determined using the "current" ratings of CAARMS and will be determined at weeks 4, 6, 12, 24, 36, 52. These current ratings are based on the patients' experience in 'the last fortnight' and are for the four positive symptoms only.
- 789 The definitions for a responder at the different time points are as follow:
- A responder at the end of Step 1 is one who shows a response at both weeks 4 and 6.
- A responder at the end of Step 2 is one who shows a response at both weeks 12 and 24.
- A responder at week 36 is one who shows a response at week 36 this is for the fast fail
 option.
- 794 Key:
- 795 UTC = Unusual Thought Content subscale of the CAARMS
- 796 NBI = Non-Bizarre Ideas subscale of the CAARMS
- 797 PA = Perceptual Abnormalities subscale of the CAARMS
- 798 DS = Disorganised Speech subscale of the CAARMS
- 799 SOFAS = Social and Occupational Functioning Assessment Scale

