- the psychological therapy.

Medical Review

1105

- 1106 All clients will undergo a medical review before the end of Step 1. Additionally, during the
- standard weekly clinical reviews held across all the sites, both clinicians and research
- assistants will present and discuss current clients with the study doctor. Based on this review
- process, the study doctor will exercise their clinical judgement to decide when a client
- 1110 requires urgent medical review and will liaise with site and study staff to see the client
- accordingly. After the M12 Intervention period participants will also have the opportunity to
- be reviewed by the STEP Study Doctor from M13 onwards, as needed. This is not included as
- a study assessment but rather an appointment available to the young person to assist in
- their ongoing clinical management and also their engagement in the STEP study, prior to
- their follow up interviews. This appointment is not compulsory but all participants will be
- informed of this opportunity at their M12 assessment and given the choice to schedule in
- 1117 this appointment for the following month. Future appointments after M13 with the Study
- 1118 Doctor may be booked in as required.

1119 Other

- Neurocognition (optional) will be conducted at baseline, 6M (W24) and M12 (W 52).
- Research bloods will be collected at baseline, M6 (W 25) and M12 (W 52).
- The DNA sample (15ml of blood or a sample of saliva will be collected at baseline. CSF
- 1123 (optional) for research and genetic analyses will be conducted during Step 2 (approximately
- 1124 Week 18), and prior to Week 52. Prior to the lumbar puncture being performed, routine
- clinical safety bloods will be collected and reviewed to ensure the participant's blood clots
- 1126 normally. Participants will also be required to have had a brain Magnetic Resonance Imaging (MRI)
- scan in the 6-12 months prior to the first Lumbar Puncture to exclude an intracranial mass lesion,
- 1128 hydrocephalus, or any other structural contraindication to having a Lumbar Puncture performed.
- Hair cortisol samples will be collected at baseline, W12, W25 and W52.
- 1130 Therapeutic alliance scales (Working Alliance Inventory) will be completed by both the
- client and the clinician at M6 (Week 24) and M12 (Week 52). The purpose of including these
- scales is to investigate whether the effect of psychological treatment is

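### H2b-H2d and the responder-subset question rest on associations within one arm or within responders, and alliance is first read at the outcome visit, so none of them alone can show a CBCM-specific mechanism

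*Protocol*

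**What the plan says.** Section 4.3 of the protocol names, as a secondary aim, the testing of biological and psychological variables as moderators and mediators of response. Section 4.4 then gives three secondary hypotheses for Step 2. H2b reads "In the CBCM group, baseline cognitive biases and vulnerabilities will predict response and outcome". H2c and H2d continue within that group: "those with better outcome and responders will show a significantly greater change on these variables than those with worse outcome", and likewise against non-responders. None of the three mentions SPS.

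The mechanism question is put to a selected group. The synopsis says "In the subset of responders to a specific intervention, we will examine whether it is likely that the treatment was effective" through the proposed mechanisms. Section 4.5.3 opens the same way ("In the subset of responders to a specific intervention, such as" CBCM or antidepressants), and the design description repeats it for responders to an "intervention such as CBCM or antidepressants, we will address whether the treatment is" working as proposed.

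Other sentences are wider. The synopsis and section 4.5.3 also plan measurements "to test whether these variables moderate or mediate response to treatment", with no limit to an arm or to responders. On therapeutic alliance, section 4.5.3 will "also investigate whether response to SPS or CBCM in Step 2 is mediate/moderated by" the quality of the relationship, which covers both Step 2 arms.

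On timing, section 7 has the Working Alliance Inventory completed by the "client and the clinician at M6 (Week 24) and M12 (Week 52"). Section 7.1.2 gives DACOBS at baseline, week 6, week 24 and month 12. Section 5.2.1 places the primary endpoint at 6 months, the end of Step 2, which the schedule shows as week 24.

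**The concern.** A moderator of CBCM is a variable whose relation to outcome differs between CBCM and its control. A mediator is a variable that treatment shifts and that then shifts outcome. Both need the randomised comparison. A correlation seen only within CBCM would look the same if DACOBS predicted outcome equally well under SPS.

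The protocol's own background makes that plausible. Section 4.1 cites an earlier trial in which supportive therapy gave the same degree of symptomatic and functional improvement as CBT. The same section calls the link between CBT and cognitive bias a focus of the design.

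Restricting to responders adds a second difficulty. Response is a post-randomisation outcome, and within that subset it no longer varies, so there is nothing for a mechanism variable to explain.

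Alliance raises a separate question of time order. A first reading after 18 weeks of Step 2 therapy is not a baseline characteristic. When it is taken at the outcome visit, improvement may have shaped the alliance rather than the reverse.

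At stake is the secondary aim. Findings of general prognosis could be reported as evidence of how CBCM works and for whom, although a concurrent randomised SPS control exists.

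**Working it through.** **Plan figure used.** The protocol attaches no calculation to these hypotheses. The only planned number needed is the Step 2 sample in section 6.2: 500 × 0.5 (Step 1 non-response) × (1 − 0.2) (drop-out) = 200, which reproduces.

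**Assumptions, none stated in the protocol.** Allocation is 1:1, giving 100 per arm. Tests are two-sided at 0.05. The variable correlates r = 0.2, 0.3 or 0.4 with outcome, equally in both arms. It is purely prognostic, with no arm interaction and no arm effect on it.

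**Within-CBCM test of H2b, by formula.** Fisher z = atanh(r), with SE = 1/√(100 − 3) = 0.1015.

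- r = 0.2: 0.2027/0.1015 = 2.00; power = Φ(2.00 − 1.96) ≈ 0.52
- r = 0.3: 0.3095/0.1015 = 3.05; power = Φ(3.05 − 1.96) ≈ 0.86
- r = 0.4: 0.4236/0.1015 = 4.17; power = Φ(4.17 − 1.96) ≈ 0.99

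**Simulation, 4,000 runs per row.** The H2c/H2d column treats the variable as a change score and compares better with worse outcome at the median within CBCM. A half split matches the 50% Step 2 non-response that section 6.2 assumes.

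| r | H2b test, CBCM only | Arm × variable interaction, n = 200 | H2c/H2d type, CBCM only | Arm effect on the variable, n = 200 |
|---|---|---|---|---|
| 0.2 | 52% | 5.0% | 36% | 5.2% |
| 0.3 | 86% | 5.2% | 67% | 5.3% |
| 0.4 | 99% | 4.7% | 91% | 4.9% |

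The Monte Carlo standard error near 5% is √(0.05 × 0.95/4000) = 0.3 percentage points, so both two-arm columns sit at the nominal level.

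**Timing, side by side.**

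| Item | Readings |
|---|---|
| Step 2 randomisation | week 6 |
| Alliance | weeks 24 and 52 |
| DACOBS | baseline, weeks 6, 24 and 52 |
| 6-month functioning (primary) | week 24 |

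Alliance has no reading before the primary outcome. DACOBS has readings up to randomisation, so its baseline value can serve as a moderator. Its first reading under the allocated Step 2 treatment coincides with the primary outcome.

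**The case against.** **Wording of H2b.** It speaks of prediction, not moderation. If DACOBS correlates with outcome in both arms, H2b as written is true, and 52% to 99% is power for a true statement. A reader might take those figures as false-positive rates, and that would be wrong. What they show is that a significant H2b says nothing about specificity to CBCM. This matters because the design description sets out the same expectation, that responders start with more prominent biases which then improve, under the label of moderators and mediators of response.

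**Scope.** A reader might infer that moderation and mediation are tested only within CBCM or only in responders. The documents do not support that: the unrestricted aim and the two-arm alliance question stand beside the narrower sentences. H2d also contrasts responders with non-responders, so not every mechanism question lacks variation in response.

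**The SAP.** The model may be specified there, and a few lines of section 14.1 are missing from the copy at hand. The absence of an interaction model from the protocol is therefore no fault. But the protocol does state the populations for H2b-H2d and the assessment times, and no SAP can supply alliance readings before week 24.

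**Alliance.** Calling the week-24 reading useless would go too far. It precedes 12-month functioning, and section 7 also wants it to track alliance over time. By month 12, however, participants have moved on to Step 3 or to the relapse-prevention randomisation, so that outcome no longer isolates the Step 2 contrast.

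**Rank.** Section 4.5.3 classes the responder and alliance questions as exploratory. That limits the weight of the point.

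**Conclusion.** The point holds in a limited form. H2b-H2d and the responder-subset analysis cannot by themselves separate a CBCM-specific effect from general prognosis. With 100 per arm and a purely prognostic variable at r = 0.2 to 0.4, H2b would be supported in about 52% to 99% of trials, and comparisons of the H2c/H2d type in about 36% to 91%. Tests that use both randomised arms stay near 5%. The correlation range, the allocation ratio and the two-sided tests are assumptions, and the size moves strongly with the correlation.

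For the 6-month outcome, week-24 alliance is neither a baseline moderator nor a time-ordered mediator. DACOBS change shares the mediator problem, though baseline DACOBS remains usable as a moderator.

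The protocol does not rule out the better analysis. Its wider statements allow it, and the schedule does not restrict DACOBS to CBCM. The primary analysis of 6-month functioning is unaffected. This is a worthwhile and cheap correction to secondary and exploratory aims.

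**What to change.** - Base any moderation claim on a baseline DACOBS by Step 2 arm interaction in all participants randomised in Step 2. H2b can stay as a statement of prediction.
- Test the arm effect on DACOBS change with the randomised contrast. Report any mediation estimate as lacking time order, because the first post-randomisation DACOBS reading falls at the outcome visit.
- Label the within-CBCM, responders-only and week-24 alliance results as associations, not as evidence of mechanism.

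This needs wording in the analysis plan and no new data.

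The cost is precision. With equal arms, the standard error of a difference between two slopes is √2 ≈ 1.4 times that of one slope. As an illustration, suppose DACOBS predicts outcome in CBCM and not at all in SPS. On the Fisher scale the SE is √(2/97) = 0.1436, so power is about Φ(0.2027/0.1436 − 1.96) = 29% for r = 0.2, Φ(0.3095/0.1436 − 1.96) = 58% for r = 0.3, and Φ(0.4236/0.1436 − 1.96) = 84% for r = 0.4. A non-significant interaction should therefore be reported with its interval and not read as absence of moderation.

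Adding an alliance reading at week 12 would need a protocol amendment and is almost certainly too late. This version is dated 6 October 2020, and the synopsis plans the last visit for January 2021 after 24 months per participant. Last entry would thus fall around January 2019, and the last week-12 visit around April 2019.
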